## LIST OF ABBREVIATIONS

Abbreviation	Definition
AE	Adverse Event
ATC	Anatomical Therapeutic Chemical
BID	Bis in die or twice daily
BMI	Body Mass Index
CRF	Case Report Form
CS	Compound Symmetry
CSR	Clinical study report
DSMB	Data Safety Monitoring Board
ECG	Electrocardiogram
EOT	End of Treatment
ePRO	Electronic Patient-Reported Outcomes
GEE	Generalized Estimating Equation
ITT	Intent-to-Treat
MedDRA	Medical Dictionary for Regulatory Activities
MMRM	Mixed-model Repeated Measures
NIAID	National Institute of Allergy and Infectious Diseases
PD	Pharmacodynamic
PK	Pharmacokinetics
PP	Per-Protocol
PT	Preferred Term
QTcF	Heart rate-corrected QT interval using Fridericia's formula
RASP	Reactive Aldehyde Species
SAE	Serious Adverse Event
SAP	Statistical Analysis Plan
SARS-CoV-2	Severe Acute Respiratory Syndrome Coronavirus-2
SOC	System Organ Class
TEAE	Treatment-Emergent Adverse Event
TESAE	Treatment-Emergent Serious Adverse Event
WHO	World Health Organization

## 1 INTRODUCTION

The purpose of this Statistical Analysis Plan (SAP) is to provide a description of the statistical methods to be implemented for the analysis of data from the study with protocol number ADX-629-COVID-19-001. The SAP will be finalized prior to database lock. Any deviations from the SAP after database lock will be documented in the final Clinical Study Report (CSR).

## 2 STUDY OVERVIEW

### 2.1 Study Objectives

#### 2.1.1 *Primary Objective*

The primary objective of this clinical trial is to evaluate the safety and tolerability of ADX-629, administered orally, in adult subjects with COVID-19 of moderate severity.

#### 2.1.2 *Secondary Objectives*

The secondary objectives of this clinical trial are the following:

- To evaluate the National Institute of Allergy and Infectious Diseases (NIAID) 8-point ordinal scale for COVID-19 scores of adult subjects with COVID-19 of moderate severity who were administered ADX-629 orally; and
- To assess the pharmacodynamics (PD) by measuring plasma reactive aldehyde species (RASP) in adult subjects with COVID-19 of moderate severity who were administered ADX-629 orally.

### 2.2 Study Design

#### 2.2.1 *Overview*

ADX-629-COVID-19-001 is a Phase 2a, randomized, double-blind, placebo-controlled, clinical trial to evaluate the safety, tolerability, efficacy, and PD of ADX-629, administered orally, in adult subjects with COVID-19 of moderate severity. Approximately 30 subjects will be randomized in a 2:1 ratio (ADX-629 to placebo) to receive either ADX-629 300 mg *bis in die* or twice daily (BID) or placebo BID for up to 28 days.

Treatment will begin on Day 1 following randomization. In addition to ADX-629 or placebo, all subjects will receive standard of care treatment for COVID-19. Treatment may commence whether a subject is hospitalized or is treated as an outpatient at Screening. During the Treatment Period (Days 1 to 28/End of Treatment [EOT]), all subjects will receive study drug (either ADX-629 or placebo) BID. The study drug will continue to be taken on an outpatient basis if a subject is discharged from the hospital prior to Day 28 for hospitalized subjects. If a subject is placed on mechanical ventilation and/or is otherwise unable to ingest an oral tablet, dosing will be stopped. However, the subject will continue to be monitored for efficacy and safety. Dosing of the study drug may resume once the subject is able to safely ingest an oral tablet.

All subjects will also have an assessment using the NIAID ordinal scale score daily on Days 1 to 28/EOT. The NIAID score will be evaluated directly for inpatient subjects and assessed via a subject diary for outpatient subjects through Day 28.

After treatment is completed, subjects will undergo a follow-up visit on Day 35 ( $\pm 3$  days) and a telephone follow-up on Day 60 ( $\pm 3$  days). The purpose of the telephone follow-up is to assess survival status and evaluate for COVID-19 relapse. A telephone follow-up visit may be performed in lieu of the Day 35 follow-up visit if the subject is unable to attend in person.

The schedule of study assessments is described in Appendix A.

#### 2.2.2 *Randomization and Blinding*

Subjects will be randomized in a 2:1 ratio to receive an oral tablet of either ADX-629 300 mg BID or placebo BID for up to 28 days. Subjects, Investigators, and clinical trial personnel (including the Sponsor/designee) involved in the administration and assessment of the study drug will be blinded to the subject treatment assignments throughout the clinical trial.

#### 2.2.3 *Study Drug*

ADX-629 and the corresponding placebo will each be available as a tablet for oral administration. The study drug will be packaged in a kit with 2 bottles, each bottle containing thirty (30) 300 mg tablets.

ADX-629 and the corresponding placebo will each be administered orally as a tablet, at the discretion of the Investigator, without food, defined as no food for at least 2 hours prior to dosing and at least 1 hour after dosing. Each subject will receive either ADX-629 300 mg BID or placebo BID for up to 28 days. If a subject is temporarily unable to tolerate dosing, a temporary dose interruption of up to 2 days may be permitted, after discussion with the Medical Monitor. No dose reductions will be permitted.

#### 2.2.4 *Sample Size Determination*

Approximately 30 subjects will be randomized in a 2:1 ratio to 1 of 2 treatment groups: ADX-629 or placebo, both with standard of care treatment for COVID-19. This clinical trial is exploratory in nature and is not formally powered.

### 3 STATISTICAL METHODOLOGY

#### 3.1 General Considerations

##### 3.1.1 *Analysis Day*

Analysis day will be calculated from the date of first dose of study drug. The day of the first dose of study drug will be Day 1, and the day immediately before Day 1 will be Day -1. There will be no Day 0.

##### 3.1.2 *Analysis Visits*

Nominal visits (i.e., study visits captured on the CRF) will be used for all efficacy and safety analyses.

##### 3.1.3 *Definition of Baseline*

Baseline is defined as the last measurement prior to the first dose of study drug.

### 3.1.4 Summary Statistics

Categorical data will generally be summarized with counts and percentages of subjects. Continuous data will generally be summarized with descriptive statistics including n (number of non-missing values), mean, median, standard deviation, minimum, and maximum.

## 3.2 Analysis Populations

### 3.2.1 Intent-to-Treat (ITT) Population

The ITT Population is defined as all randomized subjects. The ITT Population will be the primary population for analysis of secondary (efficacy) endpoints.

### 3.2.2 Per-Protocol (PP) Population

The PP Population is defined as all subjects in the ITT Population who completed the study with no major protocol deviations that may impact the key secondary endpoint. The PP Population will be a secondary population for analysis of the key secondary endpoint.

A list of subjects with major protocol deviations leading to exclusion from the PP Population will be finalized prior to unblinding the randomized treatment assignments.

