6.6 Early Termination Visit and Withdrawal Procedures

The EOT for subjects completing the clinical trial is Day 28. For subjects who are withdrawn from the clinical trial prior to completion, all Day 28 procedures (see Section 6.3.10) will be performed at an early termination visit. Subjects who are withdrawn and complete an early termination visit will also undergo a telephone follow-up at Day 60.

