9 STATISTICS

9.1 Analysis Populations

The following analysis populations are defined for this clinical trial:

- Intent-to-Treat (ITT) Population: All randomized subjects;
- Safety Population: All randomized subjects who receive at least 1 dose of study drug;
- Per-Protocol Population: All subjects in the ITT Population without major protocol deviations; and
- PD Population: All subjects who have at least 1 PD measurement.

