10.3 End of Clinical Trial

The end of the clinical trial is defined as the date when the last subject for the clinical trial has completed the Day 60 telephone visit or otherwise terminates (withdraws, is withdrawn, or dies) before the Day 60 telephone visit.

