## 3.3 Subject Data and Study Conduct

### 3.3.1 Subject Disposition

Counts and percentages of subjects who were screened (signed informed consent), discontinued early during screening (screen failures), and reasons for failed screening will be summarized based on all screened subjects.

Counts and percentages of subjects who were randomized, discontinued early from the treatment, discontinued early from the study, completed the treatment and completed the study will be summarized by treatment and in total based on all randomized subjects. Reasons for early discontinuation will also be summarized.

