### 3.4.1 Key Efficacy Endpoint

The key efficacy endpoint is the NIAID ordinal scale score (Table 1) over Day 1 through Day 28.

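### The SAP's Per-Protocol Population requires an undefined study completion, which excludes deaths by Day 28 from the second analysis of the key endpoint

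*SAP*

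**What the plan says.** Protocol 9.1 sets one condition: "Per-Protocol Population: All subjects in the ITT Population without major protocol deviations". SAP 3.2.2 starts from the same ITT subjects but admits only those "who completed the study with no major protocol deviations that may impact the key secondary endpoint". The SAP therefore adds a completion requirement and also narrows which deviations count. The only change listed in the readable text of SAP section 6 concerns laboratory summaries.

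On the role of this population, SAP 3.2.2 states: "The PP Population will be a secondary population for analysis of the key secondary endpoint". SAP 3.4 analyses all efficacy endpoints in ITT, adds PP for the key endpoint alone, and calls every assessment exploratory. On the endpoint, SAP 3.4.1 states: "The key efficacy endpoint is the NIAID ordinal scale score (Table 1) over Day 1 through Day 28". Its Table 1 gives death the lowest of eight scores, 1. The analysis set out there is a descriptive summary of the change from baseline to Day 28.

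Neither document defines completion for an individual subject. Three places bear on it:

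- SAP 3.3.1 counts separately the subjects who "discontinued early from the treatment, discontinued early from the study, completed the treatment and completed the study".
- Protocol 10.3 ends the trial when the last subject has "completed the Day 60 telephone visit or otherwise terminates (withdraws, is withdrawn, or dies) before the Day 60 telephone visit".
- Protocol 6.6 states: "The EOT for subjects completing the clinical trial is Day 28".

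**The concern.** A per-protocol set is meant to remove subjects whose conduct departed from the protocol. Dying is not a departure. Under the completion condition, though, a subject who dies leaves the set because of the outcome being measured, and that outcome is the worst category of the key endpoint. With about 20 and 10 subjects per arm, one such exclusion can move an arm mean noticeably. The arm with more deaths gains from the exclusion.

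The undefined term raises a second problem. The endpoint window closes at Day 28. If completion is judged at Day 60, subjects with complete endpoint data could be excluded for something that happens after the window.

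**Working it through.** There is no figure in the plan to reproduce: the trial is not formally powered, and the point concerns a definition. The check compares the definitions and then illustrates the size.

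**1. Who is in PP, assuming no major deviation**

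| Subject | Protocol 9.1 | SAP, completion = Day 28 | SAP, completion = Day 60 |
|---|---|---|---|
| Dies by Day 28 | in | out | out |
| Full Day 1–28 NIAID data, misses Day 60 call | in | in | out |
| Full Day 1–28 NIAID data, dies after Day 28 and before Day 60 | in | in | out |
| Withdraws before Day 28 | in | out | out |

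The first row does not depend on how completion is read. The second and third rows do.

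**2. Effect of dropping deaths on an arm mean**

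Inputs: about 30 subjects at 2:1 (SAP 2.2.4), so 30 × 2/3 = 20 on ADX-629 and 30 × 1/3 = 10 on placebo. Assumptions: common baseline b of 5 to 7, common survivor change s, and each death scored 1 at Day 28 (change 1 − b). With k deaths among n:

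- mean with deaths kept = [(n − k)s + k(1 − b)] / n
- mean with deaths dropped = s
- shift = k(s + b − 1) / n

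If every survivor ends at 8, then s = 8 − b and the shift is 7k/n, whatever the baseline:

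| Arm | k | Shift | Kept vs dropped, b = 7 | Kept vs dropped, b = 5 |
|---|---|---|---|---|
| ADX-629 (20) | 1 | 7/20 = 0.35 | (19 × 1 − 6)/20 = 0.65 vs 1.00 | (19 × 3 − 4)/20 = 2.65 vs 3.00 |
| ADX-629 (20) | 2 | 14/20 = 0.70 | 0.30 vs 1.00 | 2.30 vs 3.00 |
| Placebo (10) | 1 | 7/10 = 0.70 | (9 × 1 − 6)/10 = 0.30 vs 1.00 | (9 × 3 − 4)/10 = 2.30 vs 3.00 |
| Placebo (10) | 2 | 14/10 = 1.40 | −0.40 vs 1.00 | 1.60 vs 3.00 |

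If survivors instead improve by 1.0 from any baseline, the shift is kb/n. For one death that is 0.25 to 0.35 in the arm of 20 and 0.50 to 0.70 in the arm of 10.

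**3. Direction of the bias** (ADX-629 minus placebo, baseline 7, assumed survivor changes)

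- Survivors +1 in both arms, one ADX-629 death: kept 0.65 − 1.00 = −0.35; dropped 0. This moves toward no difference.
- ADX-629 survivors +1, placebo survivors 0, one ADX-629 death: kept 0.65 − 0 = 0.65; dropped 1.00. This moves away from no difference.
- Same survivors, one placebo death instead: placebo mean (9 × 0 − 6)/10 = −0.60, so kept 1.00 + 0.60 = 1.60; dropped 1.00. This moves toward no difference.

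**4. How likely an exclusion is**

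Protocol 1.1 reports COVID-19 fatality from below 1.0% to over 6%. The rate in this population is not given. Taking 1% and 6% for illustration, the chance of at least one death among 30 is 1 − 0.99^30 = 26% and 1 − 0.94^30 = 84%.

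Under the Day 60 reading, with assumed missed-call rates of 5%, 10% and 20%, the expected losses are 30 × rate = 1.5, 3 and 6 subjects. The chance of losing at least one is 1 − (1 − rate)^30 = 78.5%, 95.8% and 99.9%.

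**The case against.** The strongest reply is that little depends on PP. ITT is the primary efficacy population and contains everyone randomized. Mortality is a separate endpoint with randomized subjects as its denominator (SAP 3.4.2), AEs leading to death are tabulated (SAP 3.6.1), and all NIAID data are listed (SAP 3.4.1). No decision is tied to PP. All of this stands. A reader might infer that the rule conceals harm, but the documents do not support that, because deaths are visible in several other outputs. Nor does PP lose every poor outcome: survivors with scores 2 to 4 can remain.

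A reader might also take it as settled that a missed Day 60 call removes a subject. It is not. SAP 3.3.1 separates treatment completion from study completion but names no day for either. Protocol 10.3 defines the end of the whole trial, not completion by one subject. Protocol 6.6 mentions Day 28, though as end of treatment. Day 60 is the better-supported reading, but it remains an inference.

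A third inference would be that the exclusion always pulls toward no difference. Step 3 of the working shows that it does not.

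Selection after unblinding is not the problem either. SAP 5.2 finalizes population exclusions before treatment assignments are revealed.

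Finally, the illustrated gap between populations assumes that ITT counts a death as 1 at Day 28. The SAP does not say so. It analyses nominal visits (SAP 3.1.2) and counts non-missing values (SAP 3.1.4). If scores after death are simply missing, deaths also leave the ITT Day 28 mean and the gap disappears. This objection is correct, and it widens the correction needed: death scoring must be fixed for ITT as well as PP.

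**Conclusion.** The point holds in a limited form. The completion condition departs from protocol 9.1, is not declared in the readable text of SAP section 6, and excludes deaths by Day 28 whether completion is placed at Day 28 or Day 60. The loss of subjects over a missed Day 60 call is conditional on a definition that the SAP does not give.

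One dropped death moves an arm mean by about 0.25 to 0.35 points on ADX-629 and 0.50 to 0.70 on placebo. These figures rest on assumed arms of 20 and 10, baseline 5 to 7, uniform survivor outcomes and a death scored 1 at Day 28. Real survivor scores will vary, and the number of deaths is unknown.

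The consequence is confined to the interpretation of an exploratory secondary population: agreement between ITT and PP would say nothing about subjects who died. That justifies a text correction, not doubt about the trial's primary safety objective.

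**What to change.** Make three edits before unblinding:

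1. **SAP 3.2.2.** Replace the completion condition with: had NIAID follow-up through Day 28, or died before Day 28. Add that missing the Day 35 or Day 60 contact does not exclude a subject. Deleting the condition, as in protocol 9.1, is also acceptable, but it would admit early withdrawals without a Day 28 score.
2. **SAP 3.4.1.** State that a death is scored 1 from the day of death through Day 28, in both ITT and PP.
3. **SAP section 6.** Record any remaining difference from protocol 9.1, including the restriction to deviations that affect the key endpoint if it is kept.

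The cost is a few sentences. No new data, visits or analyses are needed.

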### 3.2.3 Safety Population

The Safety Population is defined as all randomized subjects who received at least one dose of study drug. All safety data will be analyzed using the Safety Population. In the event that a subject takes the wrong study drug (i.e., did not take the randomized study drug), the actual treatment received will be used for analysis.

### 3.2.4 Pharmacodynamic (PD) Population

The PD Population is defined as all subjects who have at least 1 PD measurement after at least one dose of drug.

## 3.3 Subject Data and Study Conduct

### 3.3.1 Subject Disposition

Counts and percentages of subjects who were screened (signed informed consent), discontinued early during screening (screen failures), and reasons for failed screening will be summarized based on all screened subjects.

Counts and percentages of subjects who were randomized, discontinued early from the treatment, discontinued early from the study, completed the treatment and completed the study will be summarized by treatment and in total based on all randomized subjects. Reasons for early discontinuation will also be summarized.

### 3.3.2 Protocol Deviations

Medpace Protocol Deviation Plan contains details on the key description and classification of protocol deviations (PDs). CSR-reportable PDs by deviation category will be summarized by treatment group and in total based on all randomized subjects.

All CSR-reportable PDs and COVID-19 related non-reportable PDs will be listed.

### 3.3.3 Analysis Populations

Counts and percentages of subjects in each analysis population will be summarized by treatment and in total based on all randomized subjects.

### 3.3.4 Demographic and Baseline Characteristics

The following demographic and baseline characteristics will be summarized:

- Age (years)
- Sex
- Race
- Ethnicity
- Inpatient (yes/no)
- SARS-CoV-2 test result (positive/negative)
- COVID-19 severity categorization
- Height (cm)
- Weight (kg)
- Body mass index (BMI) (kg/m^2)
- SARS-CoV-2 Variant (if available)

Demographic and baseline characteristics will be summarized with descriptive statistics or counts and percentages of subjects as appropriate by treatment and in total for all randomized subjects and each defined analysis population.

### 3.3.5 Medical History

Medical history will be coded to system organ class (SOC) and preferred term (PT) using the Medical Dictionary for Regulatory Activities (MedDRA) version 23.1. Counts and percentages of subjects with medical history by system organ class and preferred term will be summarized by treatment and in total based on all randomized subjects.

### 3.3.6 Concomitant Medications and Procedures

Concomitant medications will be coded to anatomical therapeutic chemical (ATC) class and preferred term using WHO Drug B3 Global, September 2020. For summary purposes, medications will be considered prior medications if they stopped prior to the first dose of study drug and concomitant medications if they were taken at any time after the first dose of study drug (i.e. started prior to the first dose of study drug and were ongoing or started after the first dose of study drug).

If a medication has incomplete start or stop dates, dates will be imputed to determine whether a medication should be considered prior or concomitant. If a medication start date is incomplete, the first day of the month will be imputed for missing day and January will be imputed for missing month. If a medication stop date is incomplete, the last day of the month will be imputed for missing day and December will be imputed for missing month. Incomplete start and stop dates will be listed as collected without imputation.

Counts and percentages of subjects taking prior and concomitant medications by ATC class and preferred term will be summarized by treatment and in total based on the Safety Population.

Data listings will be provided for prior & concomitant medications and concomitant procedures / non-drug therapies.

### 3.3.7 Study Drug Exposure and Compliance

Days of exposure to study drug will be calculated as date of last dose of study drug – date of first dose of study drug + 1. Note that the exposure calculation is intended to describe the length of time a subject was exposed to study drug and therefore does not take study drug interruptions into account. Days of exposure to study drug will be summarized by treatment based on the Safety Population with descriptive statistics and with counts and percentages of subjects with exposure in the following categories:

- <1 week (<7 days)
- 1 - <2 weeks (7 - 13 days)
- 2 - <3 weeks (14 – 20 days)
- 3- <4 weeks (21 – 27 days)
- $\geq$ 4 weeks ( $\geq$ 28 days)

Percent compliance to the study drug regimen will be calculated as  $100 \times$  number of actual tablets taken / number of expected tablets taken. The number of actual tablets taken will be calculated as (# of tablets dispensed - # of tablets returned). The number of tablets expected will be calculated as (date of last visit in Treatment Period [Day 28/EOT] – date of randomization + 1)  $\times$  2, i.e., the number of days study drug was expected to be taken  $\times$  2 tablets per day. Percent compliance to the study drug regimen will be summarized by treatment based on the Safety Population with descriptive statistics and with counts and percentages of subjects with compliance in the following categories:

- <80%
- 80-120%
- >120%

All study drug accountability data and study drug administration (inpatient) data will be listed.

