1.1.2 Clinical Trial of ADX-629

In addition to nonclinical safety studies, a Phase 1 safety clinical trial was conducted in 85 healthy human volunteers in a single ascending dose (SAD) clinical trial and a multiple ascending dose (MAD) clinical trial. In the SAD clinical trial, 41 subjects received ADX-629 and 13 subjects received placebo, across all dose cohorts. In the MAD clinical trial, 23 subjects received ADX-629 and 8 subjects received placebo across all cohorts. Overall, ADX-629 was found to be safe and tolerable at the doses explored, including the maximum dose of 600 mg *bis in die* or twice daily (BID). The adverse event (AE) profile of ADX-629 was favorable compared to placebo. A total of 6 (9.4%) subjects who received ADX-629 had a treatment-emergent AE (TEAE) compared to 4 (19.1%) subjects who received placebo. None of the subjects required an interruption or discontinuation of the study drug.

No clinically meaningful changes were observed in the hepatic and renal analytes, including transaminases (alanine aminotransferase [ALT] and aspartate aminotransferase [AST]), alkaline phosphatase, amylase, gamma-glutamyl transferase, bilirubin, creatinine kinase, and creatinine. No changes in serum glucose were observed. Throughout the clinical trial period, there were no clinically meaningful changes observed in heart rate, blood pressure (systolic, diastolic, and orthostatic changes), respiratory rate, pulse oximetry, or temperature. No clinically significant hematology changes were observed. ADX-629 did not lead to a prolongation of heart rate-corrected QT interval using Fridericia's formula (QTcF). There were no subjects who had a QTcF >500 ms or a change of >60 ms from baseline. Five subjects had a change of >30 ms from baseline; however, no intervention or study drug interruption or discontinuation was required, and all subjects remained asymptomatic. Three of the 5 subjects were in the SAD portion of the clinical trial (1 each in of the 100 mg, 200 mg, and 700 mg dose cohorts) and the remaining 2 subjects were in the MAD portion of the clinical trial (1 in each of the 150 mg BID and 300 mg BID dose cohorts).

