Although PK variability was observed, a linear correlation was evident in C_{max} and AUC as dose increased. The half-life was consistent across cohorts and days, with mean values in multiple day exposures ranging from 3.49 hours to 6.83 hours. Little to no accumulation of ADX-629 was observed across all cohorts. At the highest dose (600 mg BID), C_{max} was 1700 ng/mL (approximately 8.5 μ M) and AUC from time 0 to 12 hours (AUC_{0-12}) was 7220 h*ng/mL. At the closest dose to the clinical dose (350 mg BID), a C_{max} of 1180 ng/mL (approximately 5.8 μ M) and an AUC_{0-12} of 4110 h*ng/mL were consistent with an adequate molar ratio to achieve stoichiometric efficacy against elevated RASP. A decrease in free MDA levels was observed in the plasma of healthy volunteers over 10 days of oral dosing with ADX-629 600 mg BID that was statistically significantly greater than that of subjects treated with placebo. Following ingestion of a high-fat meal on Day 10 of dosing with ADX-629 600 mg BID or placebo, levels of free fatty acids were statistically significantly lower, and levels of HDL were statistically significantly higher, in ADX-629-treated subjects compared with placebo-treated subjects, potentially representing additional anti-inflammatory activity of ADX-629.

The Investigator's Brochure provides more details of the clinical trials conducted with ADX-629.

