#### *3.6.1 Adverse Events (AEs)*

AEs will be captured from the date of informed consent through study completion. All AEs will be coded to system organ class and preferred term using MedDRA version 23.1.

Treatment-emergent adverse events (TEAEs) are defined as AEs that start after the first dose of study drug. AEs with partially missing onset dates will also be included as treatment emergent when the month (if it exists) and the year occur on or later than the month and year of the first dose date.

An overview of AEs will be provided including counts and percentages of subjects (and event counts) with the following:

- Any TEAEs (overall and by maximum severity)

- Any study drug related TEAEs
- Any serious AEs (SAEs)
- Any treatment-emergent serious AEs (TESEAEs)
- Any TEAEs leading to discontinuation of study drug
- Any AEs leading to death

Counts and percentages of subjects (and event counts) will also be presented by system organ class and preferred term for each of the categories in the overview.

Listings will be presented for all AEs and hospitalization data.

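### The planned safety tables give no by-arm count of dose interruptions for intolerance, although tolerability is part of the primary objective

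*SAP*

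**What the plan says.** SAP 2.1.1 sets the primary objective: to "evaluate the safety and tolerability of ADX-629, administered orally", in adults with moderate COVID-19.

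SAP 2.2.3, like Protocol 5.5.3, provides for intolerance short of stopping: "If a subject is temporarily unable to tolerate dosing, a temporary dose interruption of up to 2 days may be permitted". The Medical Monitor must first be consulted. Both sections rule out dose reduction. SAP 2.2.1 describes a second kind of gap: dosing stops when a subject is ventilated or cannot swallow a tablet, and "Dosing of the study drug may resume once the subject is able to safely ingest an oral tablet".

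SAP 3.6.1 lists the AE overview categories: all TEAEs (overall and by maximum severity), drug-related TEAEs, SAEs, treatment-emergent SAEs, "Any TEAEs leading to discontinuation of study drug", and AEs leading to death. The tables by system organ class (SOC) and preferred term (PT) repeat these categories.

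In SAP 3.3.7, "Days of exposure to study drug will be calculated as date of last dose of study drug" minus date of first dose, plus 1. The section says this is meant to "describe the length of time a subject was exposed to study drug and therefore does not take study drug interruptions into account". It also summarises tablet-count compliance with descriptive statistics and three bands: below 80%, 80-120%, and above 120%.

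Protocol 1.1.2 reports on Phase 1: "None of the subjects required an interruption or discontinuation of the study drug".

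**The concern.** In a trial of about 30 subjects with no formal power, the descriptive safety tables are the primary result. Having to pause the drug because it cannot be tolerated is direct evidence on tolerability. With dose reduction excluded, it is the only dosing response the documents provide between continuing and stopping. The protocol's own Phase 1 summary puts interruption beside discontinuation.

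The SAP carries forward only the second of these. From its tables, a reader could not say how many subjects in each arm paused for intolerance, which events led to the pauses, or whether the Phase 1 statement can be repeated for this trial.

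**Working it through.** The documents state no figure for interruptions, so there is nothing to reproduce. The check applies the SAP's formulas to a subject with a full 28-day treatment period.

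**Inputs**
- Exposure (SAP 3.3.7): last dose date − first dose date + 1.
- Compliance (SAP 3.3.7): 100 × (tablets dispensed − tablets returned) / expected tablets.
- Expected tablets (SAP 3.3.7): days from randomisation to the last treatment-period visit, inclusive, × 2. For 28 days this is 28 × 2 = 56.
- Permitted interruption for intolerance (SAP 2.2.3): up to 2 days, or 4 tablets.
- Arm sizes (SAP 2.2.4): about 30 at 2:1, so about 20 on ADX-629 and 10 on placebo.

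**Step 1. One subject with d days off drug who finishes on Day 28.** Exposure is 28 − 1 + 1 = 28 whatever d is. Compliance is 100 × (56 − 2d)/56.

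| Days off | SAP exposure (days) | Tablets taken | Compliance | Band |
|---|---|---|---|---|
| 0 | 28 | 56 | 100.0% | 80-120% |
| 1 | 28 | 54 | 96.4% | 80-120% |
| 2 | 28 | 52 | 92.9% | 80-120% |
| 5 | 28 | 46 | 82.1% | 80-120% |
| 6 | 28 | 44 | 78.6% | <80% |

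The band is left only at 12 missed tablets: 11 missed gives 45/56 = 80.4%, and 12 gives 44/56 = 78.6%. In a shorter treatment period of T days, a 2-day pause stays in the band as long as (2T − 4)/2T ≥ 0.8, that is, T ≥ 10.

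**Step 2. Is the compliance value specific?** No. Four forgotten tablets give 52/56 = 92.9%. So does stopping for good after Day 26 and attending the Day 28 visit.

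**Step 3. Arm level.** One 2-day pause among 20 subjects lowers mean compliance by (100 − 92.86)/20 = 0.36 points. At the extreme, if all 20 paused for 2 days, the mean, median, minimum and maximum would all be 92.9%, yet all 20 would stay in the ≥4-week exposure category and the 80-120% band.

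**Step 4. A long gap.** Dosing on Days 1-4 and 25-28 is 8 dosed days. SAP exposure is 28 days (≥4 weeks). Compliance is 16/56 = 28.6%, so the subject appears in the <80% row.

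**Step 5. Table by table: does any give a by-arm count of interruptions for intolerance?**
- AE overview and SOC/PT tables (3.6.1): the event is counted; its link to a pause is not.
- Disposition (3.3.1): early discontinuation and completion only.
- Exposure (3.3.7): ignores pauses by design.
- Compliance (3.3.7): reflects missed tablets, not the reason.
- Listings (3.3.7, 3.6.1): all AEs and accountability data are listed, but dose administration is listed for inpatients only and action taken is not named as a listed field. A listing gives no rate in any case.

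**The case against.** The case for leaving the SAP alone has real content. All TEAEs are tabulated by severity and relatedness, by SOC and PT, so the events behind a pause are not lost. Compliance is summarised with descriptive statistics as well as bands, and widespread pausing would move the median, minimum and maximum. Long gaps fall in the <80% row. The protocol's primary endpoint (7.1) and AE analysis (9.2.2) do not name interruptions, so no stated commitment is broken. The only documented experience is Phase 1, with no interruptions. Some protocol text on dispensing, administration and stopping is redacted, the schedule of procedures is not shown, and the programming specifications are a separate document.

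Most of this stands, and it limits the point. It does not supply the count: SAP 3.6.1 is fully visible and lists its categories one by one, and interruption is not among them.

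A reader might go further in three ways that the documents do not support.
- *That interruptions leave no trace, so a report could claim full tolerability.* Drug-related TEAEs by severity would contradict such a claim, and compliance would shift.
- *That the exposure rule is an error because the half-life is short ("with mean values in multiple day exposures ranging from 3.49 hours to 6.83 hours").* The SAP openly defines a first-to-last-dose calendar measure, which is a conventional summary of treatment duration. For the permitted pause the difference is at most 2 of 28 days.
- *That the ≥4-week count hides long drug-free gaps.* The compliance table in the same section shows them as low compliance, though without a reason.

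**Conclusion.** The point holds in a narrow form. The planned tables cannot give the by-arm frequency of interruption for intolerance, nor identify the TEAEs that led to it, although tolerability is part of the primary objective. A permitted 2-day pause in a full treatment period leaves exposure at 28 days and compliance at 92.9%, in the same categories as an uninterrupted subject. Pauses totalling 6 or more days reach the <80% band without a reason.

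How much information is lost depends on how many subjects pause, and the documents give no rate. As an illustration only, if 3 of 20 ADX-629 subjects paused for intolerance, the missing row would read 15% (exact 95% CI 3.2 to 37.9%). A discontinuation row of 0/20 beside it would still be a correct count of a different event.

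The arithmetic assumes a 28-day treatment period, two tablets a day and accurate tablet returns. This is a reporting gap worth closing. It does not invalidate the planned safety analysis.

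**What to change.** In SAP 3.6.1, add two categories to the overview and the SOC/PT tables, by actual treatment: TEAEs leading to interruption of study drug, and TEAEs leading to interruption or discontinuation combined. The second allows a direct comparison with the Phase 1 statement.

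In SAP 3.3.7, keep the first-to-last-dose calculation but label it treatment duration. Where dates are recorded, report by arm the number of subjects with an interruption, its length and its reason, keeping intolerance apart from ventilation or inability to swallow.

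SAP section 1 places finalisation before database lock, so the rows can be prespecified; after lock they would be a documented deviation in the study report.

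The cost is a few table rows, with no new visit or procedure and no change to any dosing or interruption rule. Two limits should be stated. The case report form is not in the documents; that action taken is collected is inferred from the planned discontinuation row and from Protocol 8.1, which makes action taken with study drug a ground for reporting an abnormality as an AE. Outpatient interruption dates may also be incomplete, because dose-level data are named only for inpatients.
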